9.0 Efficacy Analyses

9.1 General Considerations

All efficacy analyses will be conducted in ITT Population in each period. All tests will be 1-sided at an alpha level of 0.05.

The Primary Analysis will be conducted after all ongoing subjects have completed Week 12, data pertaining to Period 1 has been cleaned, and a database lock has occurred for the purpose of efficacy and safety analysis in Period 1. This is the only and final efficacy analysis for Period 1.

In Period 1, all categorical variables at Week 12 and experience of flare in Period 1 will be analyzed using one sample Chi-square test comparing with historical placebo rate. Supplemental analyses will be conducted to compare in-trial data in upadacitinib group vs in-trial placebo data combined with historical placebo data for primary and secondary endpoints, and compare in-trial data in upadacitinib group vs in-trial placebo data for all categorical endpoints.

Continuous variables will be analyzed using Mixed-Effect Model Repeat Measurement (MMRM) (for endpoints other than DLQI) and Analysis of Covariance (ANCOVA) (for

DLQI) comparing with historical placebo mean change from Baseline at Week 12. Supplemental analyses will be conducted to compare in-trial data in upadacitinib group vs in-trial placebo data.

Long-term efficacy in the Period 2 will be summarized using the observed case approach.

Any subject who is randomized based on a wrong stratum will be analyzed according to the actual stratum the subject belongs to.

For variables other than PGA Skin Pain NRS, "Baseline" refers to the last non-missing observation on or before the date of the first administration of study drug or the date of randomization if no study drug is given. The "Baseline" of PGA Skin Pain NRS is defined as the last non-missing weekly average score, calculated based on the daily scores from the past 7 days (with non-missing values in 4 or more days of the 7 day period), before the date of the first administration of study drug or on or before the date of randomization if no study drug is given.

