9.3.3 Sensitivity Analyses of the Primary Efficacy Endpoint

Historical placebo data pre-selected by propensity score matching combined with in-trial placebo data will be used to estimate treatment effect of upadacitinib against placebo. Subjects with historical placebo data of HiSCR were pre-selected using propensity score matching from two Humira Phase 3 studies (M11-313 and M11-810) and the Risankizumab study (M16-833), whose study populations, entry criteria and study designs are similar to this study.

The propensity scores were estimated for all randomized subjects in this study and historical placebo subjects with selected common baseline demographics and characteristics variables:

- Age
- Gender
- Race
- Smoking status
- Baseline BMI

- Baseline AN count (abscess count and inflammatory nodule count)
- Duration of HS since diagnosis
- Baseline Hurley Stage
- Baseline draining fistula

The "nearest neighbor matching" were performed based on a distance measure, caliper, with the propensity score for each subject calculated from the logistic regression. The number of synthetic placebo subjects was determined by the simulation results, for each in-trial placebo rate assumption, with pre-determined criteria that the number of synthetic placebo subjects not to exceed 68 (approximately 3 times the number of in-trial placebo subjects) and the one-sided false positive rate was controlled at 10% (simulation details can be found in [Appendix F](#) and the list of matching subjects can be found in [Appendix G](#):

In-Trial Placebo Rate	Number of Synthetic Placebo Subjects
≤ 33%	68
>33% and ≤ 34%	23*
>34%	0

* The 23 subjects with the highest rank in [Appendix G](#) Table A will be used in the analysis.

After database lock, comparison between the in-trial data of the upadacitinib group and the in-trial placebo data combined with the pre-selected historical placebo subjects' data will be performed. Frequencies and percentages will be summarized along with 95% confidence interval (CI). Pairwise comparisons of upadacitinib vs. placebo will be made using CMH test. Point estimates, *p*-value and 95% CIs for the difference in proportions between each upadacitinib group and placebo will be provided. The stratification factors (prior exposure to anti-TNF [yes, no], Hurley Stage [$<$ III, III]) will be adjusted in the model.

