Comparison between the in-trial data of the upadacitinib group and the in-trial placebo subjects will also be performed. The analysis method will be the same as described above.

The NRI-C will be the primary approach for missing data handling in the analysis of the primary efficacy endpoint. NRI-NC and MI will be used as sensitivity analysis.

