9.4 Secondary Efficacy Analyses

9.4.1 Main Analyses of Secondary Efficacy Endpoints

The secondary endpoint NRS30, defined as the achievement of at least 30% reduction and at least 1 unit reduction from Baseline in Patient's Global Assessment (PGA) of Skin Pain (numeric rating scale [NRS]) – at worst at Week 12 among subjects with baseline NRS ≥ 3 .

NRS30 will be analyzed using the same method as for the primary endpoint and comparing with the historical placebo rate (22.5%) at Week 12. The historical placebo rate of 22.5% is assumed based on the response rate of placebo subjects from the two Humira studies (Study M11-313 and Study M11-810), who satisfied the same eligibility criteria.

The same supplemental analysis to compare upadacitinib 30 mg group vs in-trial placebo group combined with pre-selected placebo subjects' data from the three existing trials will also be performed as described in Section 9.3.3. The actual number of synthetic placebo subjects is determined as below (simulation details can be found in [Appendix F](#) and the list of matching subjects can be found in [Appendix G](#)):

In-Trial Placebo Rate	Number of Synthetic Placebo Subjects
$\leq 36\%$	68
$>36\%$ and $\leq 37\%$	23*
>37	0

* The 23 subjects with the highest rank in [Appendix G](#) Table B will be used in the analysis.

Comparison between the in-trial data of the upadacitinib group and the in-trial placebo subjects will also be performed. The analysis method will be the same as described in Section 9.3.3.

In addition, analgesic use will be handled as follows:

- Prohibited analgesic (including opioids): A subject will be counted as a non-responder from the day that the subject initiates prohibited analgesic to 5 days after the end of such analgesic use.
- Protocol-allowed analgesic use:
 - A subject who enter the study without concomitant analgesic will be counted as a non-responder from the day that the subject initiates a protocol-allowed analgesic to 2 days after the end of such analgesic use.
 - A subject who entered the study on a stable dose of a protocol-allowed concomitant analgesic will be counted as a non-responder from the first day of an analgesic dose increase to 2 days after the end of the dose increase.

The NRI-C will be the primary approach for missing data handling in the analysis of the secondary efficacy endpoint. NRI-NC will be used as sensitivity analysis.

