2.5.1 Analysis of Each Dataset

For each of the K 'complete' datasets, the Chi-square test or CMH test will be used to estimate the treatment difference versus placebo and the corresponding standard error.

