2.5.2 Synthesis of Results for Statistical Inference

For the comparison between upadacitinib 30 mg and historical placebo rate, the chi-square distributed statistics from each of the K datasets will be pooled using the procedure of Rubin (1987) and Li et al. (1991). Denote by χ_k^2 chi-square distributed statistics with l degrees of freedom estimated in each of the K imputed datasets. A pooled test statistics can be obtained as follows:

$$D_\chi = \frac{\bar{\chi}^2 - \frac{K+1}{K-1} \bar{r}_\chi}{1 + \bar{r}_\chi}$$

$$\text{where } \bar{\chi}^2 = \frac{1}{K} \sum_{k=1}^K \chi_k^2; \quad \bar{r}_\chi = \left(1 + \frac{1}{K}\right) \frac{1}{K-1} \sum_{k=1}^K \left(\sqrt{\chi_k^2} - K^{-1} \sum_{k=1}^K \sqrt{\chi_k^2}\right)^2$$

The pooled p-value for the hypothesis test based on D_χ can be obtained using F distribution with l and V_χ as numerator and denominator degrees of freedom, respectively, as follows:

$$P_\chi = Pr \left[F_{l, V_\chi} > D_\chi \right]; \quad V_\chi = l^{-\frac{3}{K}} (K-1) \left(1 + \frac{1}{\bar{r}_\chi}\right)^2$$

For the comparison between in-trial data from upadacitinib group and the in-trial placebo data combined with subject-level historical data, the results from the K 'complete' datasets will be synthesized using the SAS procedure PROC MIANALYZE, following Rubin's formula (Rubin, 1987),⁶ to derive the MI estimator of the treatment difference for the final inferences.

We fit the analysis model to the kth 'complete' dataset, denoting the estimate of the treatment difference q by $\tilde{\theta}_k$ from the kth 'complete' dataset, and denoting the corresponding estimate of the variance as V_k .

The MI estimator of q (point estimator obtained from PROC MIANALYZE), $\tilde{\theta}_{MI}$, is the average of the K individual estimators:

$$\tilde{\theta}_{MI} = \frac{1}{K} \sum_{k=1}^K \tilde{\theta}_k.$$

The estimated variance of $\tilde{\theta}_{MI}$, is a combination of the between- and within-imputation variability as follows:

$$V_{MI} = W + \left(1 + \frac{1}{K}\right) B,$$

where $W = \frac{1}{K} \sum_{k=1}^K V_k$ is the within-imputation variability and $B = \frac{1}{K-1} \sum_{k=1}^K (\tilde{\theta}_k - \tilde{\theta}_{MI})^2$ is the between-imputation variance.

It has been shown⁶ that the statistic

$$T = \frac{\tilde{\theta}_{MI} - \theta}{\sqrt{V_{MI}}}$$

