has an approximate t_v distribution where $v = (K - 1) \left(1 + \frac{W}{B}\right)^2$. Statistical inference, including hypothesis testing and confidence intervals for the treatment effect, will be based on this T-statistic.

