RUN;

PROC SORT DATA=CHISQ4 NODUPKEY;
  BY MEAN_VALUE DF RX_RESULT M MEAN_SQRT;
RUN;

/*CALCULATE P VALUE*/
DATA P_CHISQ;
  SET CHISQ4;
  DROP RX;
  DX = ((MEAN_VALUE/DF) - (M+1)*RX_RESULT/(M-1))/(1+RX_RESULT);
  VX = (DF ** (-3/M)) * (M-1) * ((1 + 1/RX_RESULT) ** 2);
  PVAL = 1 - CDF("F", DX, DF, VX);
RUN;

/*****/
/*FOR TWO SAMPLE CMH TEST*/
/*****/

/*INDIVIDUAL-LEVEL DATA --> # OF RESPONDERS & # OF SUBJECTS, TO BE READ-
IN TO PROC STDRAE */
PROC FREQ DATA=ALLF;
  BY _IMPUTATION_;
  TABLES TRT01PN*STRATA*HISCR_12/LIST NOCUM NOPRINT OUT=COUNT_TABLE;
RUN;
DATA COUNT_TABLE; SET COUNT_TABLE;
  DROP PERCENT;
RUN;
PROC TRANSPOSE DATA=COUNT_TABLE OUT=FREQ_TABLE PREFIX=RESP;
  ID HISCR_12;
  BY _IMPUTATION_ TRT01PN STRATA;
  VAR COUNT;
RUN;
DATA FREQ_TABLE1; SET FREQ_TABLE;
  CASE=RESP1;
  SIZE=SUM(RESP0, RESP1);
  KEEP _IMPUTATION_ TRT01PN STRATA CASE SIZE;
RUN;

/*CALCULATE THE COMMON RISK DIFF FOR EACH COMPLETE DATASET*/
PROC STDRAE DATA=FREQ_TABLE2
  METHOD=MH STAT=RISK EFFECT=DIFF;
```

```
BY _IMPUTATION_;  
POPULATION GROUP=TRT01PN EVENT=CASE TOTAL=SIZE;  
STRATA STRATA / ORDER=DATA STATS (CL=NONE) EFFECT;  
ODS OUTPUT EFFECT=EFFECT;  
RUN;  
  
/*COMBINING RESULTS USING PROC MIANALYZE*/  
/*****  
PROC MIANALYZE DATA=EFFECT;  
  ODS OUTPUT PARAMETERESTIMATES=RISK_DIFF_MH;  
  MODELEFFECTS RiskDiff;  
  STDERR StdErr;  
RUN;
```

Appendix F. Simulations for Combining Subject-level Historical Placebo Data with In-trial Placebo Data

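### SAP 9.3.3 names a stratified CMH test for upadacitinib versus in-trial placebo, but Appendix E tests a Wald T on the Mantel-Haenszel risk difference; at 45:23 the two differ, and the printed code leaves the p-value undetermined

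*SAP*

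**What the plan says.** SAP 9.3.3 specifies, with adjustment for prior anti-TNF exposure and Hurley stage: "Pairwise comparisons of upadacitinib vs. placebo will be made using CMH test". It first applies this to upadacitinib versus in-trial plus matched historical placebo. For upadacitinib versus in-trial placebo alone it adds: "The analysis method will be the same as described above". SAP 9.4.1 does the same for NRS30: "The analysis method will be the same as described in Section 9.3.3". On the level, 9.1 states: "All tests will be 1-sided at an alpha level of 0.05". Section 13.0 repeats one-sided 0.05 for every endpoint.

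Appendix E describes what is computed. In 2.5.1 the CMH step supplies an estimate: "CMH test will be used to estimate the treatment difference versus placebo and the corresponding standard error". In 2.5.2 the results from the K "datasets will be synthesized using the SAS procedure PROC MIANALYZE", and T is the pooled difference divided by its standard error: "Statistical inference, including hypothesis testing and confidence intervals for the treatment effect, will be based on this T-statistic". The code in 3.0, under a heading that calls it a two-sample CMH test, runs PROC STDRATE with "METHOD=MH STAT=RISK EFFECT=DIFF" and passes the difference and its standard error to PROC MIANALYZE.

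Appendix F 3.1 and 3.2 give simulated power and one-sided false-positive rates, including an In-Trial Only column at 45:23 with no borrowing. Appendix F does not name the test.

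**The concern.** The test named in the body and the test specified in the appendix are different tests. In large samples this would hardly matter. Here the placebo arm has 23 subjects in four strata, two of which hold about one and two placebo subjects. A Wald statistic takes its variance from the observed proportions, so a stratum-arm with no responders adds no variance. CMH uses the null hypergeometric variance.

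This is the only purely randomized, concurrent efficacy comparison for HiSCR and NRS30. Readers will use it to check the result against the fixed historical rate. Someone reading 9.3.3 would take its p-value as a 5% CMH test, and two programmers, one following 9.3.3 and one following Appendix E, could reach opposite conclusions from the same data.

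**Working it through.** **Inputs.** Arm sizes of 45 and 23, the strata and the 2:1 allocation come from Appendix F 2.1. The stated stratum shares (5, 10, 55, 35%) sum to 105%, so they were rescaled, giving upadacitinib 2/4/24/15 and placebo 1/2/12/8. Placebo rates and the upadacitinib rates for power (59% HiSCR, 46% NRS30) come from Appendix F 3.1 and 3.2. Assumptions: equal rates across strata, no missing data, rejection at z > 1.645, 400,000 runs per rate. Stratum-arms with no responders count as zero events unless stated.

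**Formulas.** With n1, n0 the arm sizes, N their sum, m the total responders in a stratum and w = n1·n0/N:
- MH risk difference: RD = Σw(p1−p0)/Σw.
- Plug-in Wald: T = RD/SE, with SE² = Σw²[p1(1−p1)/n1 + p0(1−p0)/n0]/(Σw)². The Sato variance was run as an alternative.
- CMH: z = Σ(a − n1·m/N)/√Σ[n1·n0·m(N−m)/(N²(N−1))], with a the upadacitinib responders.

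**One-sided false-positive rate against Appendix F, In-Trial Only**

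| Endpoint, rate | SAP | Plug-in Wald | Sato Wald | CMH |
|---|---|---|---|---|
| HiSCR 18% | 0.082 | 0.088 | 0.073 | 0.046 |
| HiSCR 23% | 0.075 | 0.083 | 0.069 | 0.047 |
| HiSCR 28% | 0.072 | 0.080 | 0.067 | 0.048 |
| HiSCR 33% | 0.070 | 0.076 | 0.064 | 0.048 |
| HiSCR 34% | 0.070 | 0.075 | 0.064 | 0.048 |
| HiSCR 38% | 0.069 | 0.072 | 0.062 | 0.048 |
| NRS30 16% | 0.094 | 0.093 | 0.076 | 0.047 |
| NRS30 21% | 0.084 | 0.084 | 0.071 | 0.047 |
| NRS30 26% | 0.077 | 0.080 | 0.068 | 0.047 |
| NRS30 31% | 0.077 | 0.077 | 0.066 | 0.048 |
| NRS30 36% | 0.073 | 0.074 | 0.063 | 0.049 |
| NRS30 37% | 0.073 | 0.072 | 0.062 | 0.048 |

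All 12 SAP entries exceed 0.05. With 10,000 simulations the standard error at 5% is √(0.05×0.95/10,000) ≈ 0.002, so this is not simulation noise.

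**Power.** HiSCR at 18/23/28/33/34/38%: SAP 0.977/0.926/0.837/0.701/0.672/0.549; plug-in Wald 0.976/0.926/0.836/0.708/0.681/0.553; CMH 0.962/0.898/0.791/0.651/0.621/0.493. Plug-in Wald is within 0.9 points throughout. For NRS30 neither test fully reproduces the SAP: plug-in Wald is 2.2-4.4 points low and CMH 7.5-12.1 points low.

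**Worked example.** Responders 1, 2, 10, 6 (19/45) versus 0, 0, 3, 2 (5/23).
- Weights 0.667, 1.333, 8, 5.217; sum 15.217. Stratum differences 0.5, 0.5, 0.167, 0.15.
- Σw(p1−p0) = 0.333 + 0.667 + 1.333 + 0.783 = 3.116, so RD = 3.116/15.217 = 0.205.
- Plug-in variance of that sum: 0.056 + 0.111 + 1.648 + 1.073 = 2.888. T = 3.116/√2.888 = 1.83, p = 0.033 (Sato p = 0.036).
- CMH has the same numerator, 19 − 15.884 = 3.116, with variance 0.222 + 0.356 + 1.898 + 1.237 = 3.713. z = 3.116/√3.713 = 1.62, p = 0.053.

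The difference lies wholly in the variance.

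**The printed code.** Counts come from PROC FREQ output and are transposed, and CASE is set to RESP1. A stratum-arm with no responders has no RESP1 record, so CASE is missing rather than 0. PROC STDRATE then reads FREQ_TABLE2, but only FREQ_TABLE1 is created. With these strata, at least one such cell occurs in 88-99.6% of null runs. If those strata drop out (an assumption about how PROC STDRATE treats missing events), size is 0.011-0.046 and HiSCR power at 59% versus 28% is about 0.72. In the example only the last two strata remain: 2.116/√(1.648 + 1.073) = 1.28, p = 0.10.

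**Imputation.** K = 30, with an assumed 5-10% of outcomes imputed by a simple beta-binomial model per arm (not the SAP's count regression), at 18/28/38%: plug-in T 0.071-0.084, Sato T 0.061-0.075, pooled signed CMH z 0.046-0.050.

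**The case against.** A reader might infer that the test as coded has a size of 6-9%. The documents do not support that. The figure needs empty responder cells to be zero-filled, which the printed code does not show; if those strata drop out, the test is conservative. The undefined FREQ_TABLE2 may stand for an unprinted zero-filling step, and the Appendix F rates fit zero-filling better, but neither settles the matter.

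A reader might also infer that Appendix F was run with the Wald test. That is only an inference: no test is named, the HiSCR rates lie between the two variance forms, and NRS30 power is not reproduced.

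It is fair to say that Appendix E is open about its method, that 2.5.2 introduces T for the combined comparison, and that the false-positive rates are printed for anyone to see. But 9.3.3 and 9.4.1 carry the method to the in-trial comparison, and nothing tells the reader of 9.3.3 that no CMH statistic is used. Under NRI-NC nothing is imputed, so CMH can be run directly; that leaves the NRI-C and MI results in question.

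The 10% false-positive criterion in Appendix F governs how many matched subjects are added. It does not replace the 5% level in 9.1. That this is supplementary work in a proof-of-concept study limits the consequence but does not remove the contradiction.

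**Conclusion.** The mismatch stands on the text alone. Its size is conditional. With zero-filling, one-sided size is 0.072-0.093 (plug-in) or 0.062-0.076 (Sato) against 0.046-0.049 for CMH, and 95% Wald CI coverage under the null is 91.7-92.2% or 93.2-93.8%. Without zero-filling, size is about 1-5%. The plan as printed does not determine which applies.

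The reach is narrow: the supplementary in-trial-only p-value and CI for HiSCR and NRS30. A reader might infer that the trial's main conclusion is at risk, but the primary one-sample test against 25% does not use this statistic, and neither do the MMRM and ANCOVA comparisons. The combined comparison hardly changes: at 28% with 68 matched subjects, plug-in Wald and CMH both give 0.052. In the branch with no borrowing, the plug-in Wald false-positive rate at the rates checked was 0.4% or less for HiSCR (at least 8/23 placebo responders) and 0.06% or less for NRS30 (at least 9/23).

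**What to change.** - Take the one-sided p-value from the signed stratified CMH statistic named in 9.3.3. Compute it directly where nothing is imputed, as under NRI-NC. Pool it on the z scale, with within-imputation variance 1, under NRI-C and MI. Appendix E already pools test statistics for the one-sample test.
- Keep the MH risk difference as the estimate. Either state that its Wald CI may disagree with the CMH p-value or use a score-type CI.
- Correct the Appendix E code so that empty responder cells are set to 0 and the dataset name matches.
- Name the test in Appendix F and restate the In-Trial Only false-positive rates and power.
- If the Wald test is kept, name it in 9.3.3 and report its simulated size under the final code.

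The cost is a short SAP wording and code change and a lower stated in-trial power (HiSCR at 59% versus 28%: about 0.79 instead of 0.837). The primary analysis, the sample size and the numbers of matched subjects do not change.

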3.0 Sample SAS Code

```

/*****/
/*IMPUTATION ALGORITHM*/
/*****/
/*NOTE: THIS APPROACH REQUIRES NO MISSING IN CATEGORICAL COVARIATES AND
REQUIRES AT LEAST ONE OBSERVATION IN BASELIBE OR ONE OF THE POST-
BASELINE VISIT*/

/*PRE-AUGMENTATION - CREATE DUMMY FOR CATEGORICAL VARIABLES*/
/*****/
DATA COUNT_2; SET COUNT;
  /*THE MCMC STATEMENT BELOW ASSUMES MULTI-VARIATE NORMAL*/
  /* USE ALL DATA IN THE IMPUTATION MODEL*/
  IF HURLEY=1 THEN HURLEY1 = 1 ELSE HURLEY1 = 0; /* CREATE DUMMY
VARIABLE FOR HURLEY STAGE 1*/
  IF HURLEY=2 THEN HURLEY2 = 1 ELSE HURLEY2 = 0; /* CREATE DUMMY
VARIABLE FOR HURLEY STAGE 2*/
RUN;

/*AUGMENTATION STEP -- TO HAVE 30 MONOTONE MISSING DATASETS*/
PROC MI DATA= COUNT_2 OUT= COUNT_MONO NIMPUTE=30 SEED= 1001 /*RANDOM
SEED PRE-DEFINED*/
  ROUND=. . . . 1 1 1 1 1 /*VALUE ROUND TO INTEGER*/
  MIN=. . . . 0 0 0 0 /*MINIMUM VALUE OF COUNT IS 0*/
  MAX=. . . . . /*MAXIMUM VALUE*/
MCMC IMPUTE=MONOTONE ;
/*NOTE: CATEGORICAL VARIABLES SUCH AS HURLEY1 HURLEY2 ARE DUMMY, CREATED
ABOVE*/
/*NOTE: ALL OTHER NON-DUMMIED COVARIATES MUST BE CONTINUOUS*/
VAR TRT01PN TNFN HURLEY1 HURLEY2 BASE WK2 WK4 WK8 WK12;
/*CAUTION TO USE THE "BY" STATEMENT IN MCMC: */
/*MVN MODEL IS FITTED WITHIN EACH 'BY' GROUP, INSTEAD OF ACROSS ALL
GROUPS*/
RUN;

/*IMPUTATION STEP - DETERMINE IMPUTATION DISTRIBUTION AND RANDOMLY
IMPUTE MISSING VALUE TO GENERATE 'COMPLETE' DATASETS*/
/*****/
PROC MI DATA= COUNT_MONO OUT= COUNT_FULL NIMPUTE=1 SEED= 9001 /*RANDOM
SEED PRE-DEFINED*/

```

```
ROUND=. . . 1 1 1 1 1 /*VALUE ROUND TO INTEGER*/
MIN=. . . 0 0 0 0 0 /*MINIMUM VALUE OF COUNT IS 0*/
MAX=. . . . . . . /*MAXIMUM VALUE*/
MINMAXITER=1000;
/*CLASS CATEGORICAL VARIABLES*/
CLASS TRT01P TNFN HURLEY;
VAR TRT01P TNFN HURLEY BASE WK2 WK4 WK8 WK12;
MONOTONE REG (WK2 WK4 WK8 WK12); /* IMPUTED SEQUENTIALLY, FROM WK 1
TO 16, WITH COVARIATES CONSTRUCTED FROM THE CORRESPONDING PRECEDING
VARIABLES*/
BY _IMPUTATION_ ; /*FOR EACH OF THE 30 MONOTONE
MISSING DATASETS, IMPUTE A 'COMPLETE' DATASET*/
RUN;

/*We will get the imputed "complete" datasets for abscess, inflammatory
nodule, and draining fistula counts. For sample code below, we denote
the following variables: ABS12, INF12 and DRA12 as the corresponding
lesion count at Week 12; and AN12 as the sum of ABS12 and INF12.
Determine the HiSCR status at Week 12. */
DATA ALL; SET COUNT_FULL;
IF 0<= AN12 <=0.5*AN_BASE AND ABS12<=ABS_BASE AND DRA12 <= DRA_BASE
THEN HISCR_12=1;
ELSE HISCR_12=0;
RUN;

/*****
*/
/* DATA HANDLING STEPS TO MERGE COVID-19 STATUS OMITTED
*/
/* PLACE TO ADD DATA HANDLING AND MERGING STEPS
*/
/*****
*/

/*FOR MI, SKIP THE FOLLOWING CODE, PROCEED TO THE CODE AFTER ANALYSIS
MODEL *//*OVERRIDE MISSING VALUES NOT DUE TO COVID-19 WITH TRADITIONAL
NRI*/
DATA ALLF; SET ALL;
/*COVID19_XX='Y' IF MISSING AT WEEK XX IS DUE TO COVID-19; IF NOT,
OVERRIDE WITH TRADITIONAL NRI*/
/*VARIABLE HISCR_NRI_12: TRADITIONAL NRI DATA AT WEEK 12, WHICH COVERS
THE SPECIAL HANDLING SUCH AS THE BEFORE-AND-AFTER EXCEPTION IN THE
PARTICULAR STUDY PERIOD*/
IF COVID19_MISS NE 'Y' THEN HISCR_12 = HISCR_NRI_12;
RUN;
PROC SORT DATA=ALLF; BY _IMPUTATION_ SUBJID; RUN;
```

```
/******  
/*ANALYSIS MODEL*/  
/******  
  
/*KEY CODE: ANALYZING EACH 'COMPLETE' DATASET*/  
  
/******  
/******  
/*FOR ONE SAMPLE CHI-SQUARE TEST*/  
/******  
  
ODS OUTPUT ONEWAYCHISQ=CHI;  
PROC FREQ DATA=ADEFF;  
  BY _IMPUTATION_;  
  TABLES CRIT2FN/CHISQ TESTP=(0.75 0.25) ;  
RUN;  
  
DATA CHI;  
  SET CHI;  
  KEEP _IMPUTATION_ NVALUE1 LABEL1;  
RUN;  
  
/*GET CHI-SQUARE STATISTICS*/  
DATA CHISQ_VALUE;  
  SET CHI(WHERE = (LABEL1 = "Chi-Square"));  
  VALUE = NVALUE1;  
  DROP NVALUE1;  
RUN;  
  
/*GET DEGREE OF FREEDOM*/  
DATA CHISQ_DF;  
  SET CHI(WHERE = (LABEL1 = "DF"));  
  DF = NVALUE1;  
  DROP NVALUE1;  
RUN;  
  
DATA CHISQ;  
  MERGE CHISQ_VALUE CHISQ_DF;  
  BY _IMPUTATION_;  
  A=1;  
RUN;  
  
/*CALCULATE MEAN OF CHI-SQUARE STATISTICS*/  
PROC MEANS DATA = CHISQ MEAN NOPRINT;  
  VAR VALUE;  
  OUTPUT OUT = M_CHISQ MEAN = M_VALUE N = COUNT;  
RUN;  
  
DATA M_CHISQ;
```

```
SET M_CHISQ;  
A=1;  
RUN;  
  
DATA CHISQ1;  
MERGE CHISQ M_CHISQ;  
BY A;  
MEAN_VALUE = M_VALUE;  
M = COUNT;  
DROP _FREQ_ _TYPE_ M_VALUE COUNT;  
RUN;  
  
DATA TEMP;  
SET CHISQ1;  
SQRT_VALUE=SQRT(VALUE);  
RUN;  
  
/*CALCULATE MEAN OF SQUARE ROOT OF CHI-SQUARE STATISTICS*/  
PROC MEANS DATA = TEMP MEAN NOPRINT;  
VAR SQRT_VALUE;  
OUTPUT OUT=M_CHISQ1 MEAN=M_SQRT_VALUE;  
RUN;  
  
DATA M_CHISQ1;  
SET M_CHISQ1;  
A=1;  
RUN;  
  
DATA CHISQ2;  
MERGE CHISQ1 M_CHISQ1;  
BY A;  
MEAN_SQRT=M_SQRT_VALUE;  
DROP _FREQ_ _TYPE_ M_SQRT_VALUE;  
RUN;  
  
DATA CHISQ3;  
SET CHISQ2;  
RX = (1+1/M) * ((VALUE**0.5) - MEAN_SQRT)**2 / (M-1);  
RUN;  
  
/*CALCULATE MEAN OF RX*/  
PROC MEANS DATA = CHISQ3 MEAN NOPRINT;  
VAR RX;  
OUTPUT OUT = T_RX SUM = T_RX;  
RUN;  
  
DATA T_RX;  
SET T_RX;  
A=1;
```

```
RUN;

DATA CHISQ4;
  MERGE CHISQ3 T_RX;
  BY A;
  RX_RESULT = T_RX;
  DROP _FREQ_ _TYPE_ T_RX;
RUN;

PROC SORT DATA=CHISQ4 NODUPKEY;
  BY MEAN_VALUE DF RX_RESULT M MEAN_SQRT;
RUN;

/*CALCULATE P VALUE*/
DATA P_CHISQ;
  SET CHISQ4;
  DROP RX;
  DX = ((MEAN_VALUE/DF) - (M+1)*RX_RESULT/(M-1))/(1+RX_RESULT);
  VX = (DF ** (-3/M)) * (M-1) * ((1 + 1/RX_RESULT) ** 2);
  PVAL = 1 - CDF("F", DX, DF, VX);
RUN;

/*****/
/*FOR TWO SAMPLE CMH TEST*/
/*****/

/*INDIVIDUAL-LEVEL DATA --> # OF RESPONDERS & # OF SUBJECTS, TO BE READ-
IN TO PROC STDRAE */
PROC FREQ DATA=ALLF;
  BY _IMPUTATION_;
  TABLES TRT01PN*STRATA*HISCR_12/LIST NOCUM NOPRINT OUT=COUNT_TABLE;
RUN;
DATA COUNT_TABLE; SET COUNT_TABLE;
  DROP PERCENT;
RUN;
PROC TRANSPOSE DATA=COUNT_TABLE OUT=FREQ_TABLE PREFIX=RESP;
  ID HISCR_12;
  BY _IMPUTATION_ TRT01PN STRATA;
  VAR COUNT;
RUN;
DATA FREQ_TABLE1; SET FREQ_TABLE;
  CASE=RESP1;
  SIZE=SUM(RESP0, RESP1);
  KEEP _IMPUTATION_ TRT01PN STRATA CASE SIZE;
RUN;

/*CALCULATE THE COMMON RISK DIFF FOR EACH COMPLETE DATASET*/
PROC STDRAE DATA=FREQ_TABLE2
  METHOD=MH STAT=RISK EFFECT=DIFF;
```

```
BY _IMPUTATION_;  
POPULATION GROUP=TRT01PN EVENT=CASE TOTAL=SIZE;  
STRATA STRATA / ORDER=DATA STATS (CL=NONE) EFFECT;  
ODS OUTPUT EFFECT=EFFECT;  
RUN;  
  
/*COMBINING RESULTS USING PROC MIANALYZE*/  
/*****  
PROC MIANALYZE DATA=EFFECT;  
  ODS OUTPUT PARAMETERESTIMATES=RISK_DIFF_MH;  
  MODELEFFECTS RiskDiff;  
  STDERR StdErr;  
RUN;
```

Appendix F. Simulations for Combining Subject-level Historical Placebo Data with In-trial Placebo Data

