2.0 Study Design and Objectives

2.1 Objectives, Hypotheses and Estimands

The primary objective of this study is to assess the efficacy and safety of upadacitinib 30 mg QD in adult subjects with moderate to severe HS. The primary efficacy objective will be assessed based on the achievement of HiSCR after 12 weeks of treatment with upadacitinib 30 mg when compared to placebo in the Intent-to-Treat (ITT) population, which consists of all randomized subjects.

Hypothesis corresponding to the primary endpoint is:

- The proportion of subjects achieving HiSCR with upadacitinib is greater than that with placebo at Week 12.

The estimand corresponding to the primary endpoint is defined using composite variable strategy:

- Achievement of HiSCR at Week 12 without the initiation of antibiotics for HS-related infections and without premature discontinuation of study drug due to lack of efficacy prior to Week 12.

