2.4 Sample Size Determination

The primary endpoint is the achievement of HiSCR at Week 12. The primary analysis compares the proportion of subjects achieving HiSCR response to that of historical placebo (25% HiSCR response). Assuming the Week 12 HiSCR response rate is 57% for the upadacitinib 30 mg arm, 40 subjects on upadacitinib will provide more than 95% power with a one-sample Chi-square test and one-sided alpha = 0.05 significance level.

The historical placebo rate of 25% is assumed based on the response rate of placebo subjects satisfying the same eligibility criteria from the two Humira studies (Study M11-313 and Study M11-810).

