- Multiple Imputation (MI), a sensitivity analysis for the primary endpoint. Markov Chain Monte Carlo (MCMC) will be first applied to augment data into monotonic missing pattern and PROC MI will be used to generate 30 datasets using the regression method. Taking abscess count as an example, the variables to be included in the imputation model are: major stratum (prior exposure to anti-TNF [yes, no], Hurley Stage [< III, III]), Baseline, and measurements at each visit up to the end of the Period 1. The random seed for MCMC and the random seed for PROC MI are specified in [Appendix D](#). The imputed post-baseline measurements will be rounded to the same precision as the observed data. The same imputation strategy will be applied to the inflammatory nodule count and the draining fistula count. HiSCR status will be determined accordingly. Using the one sample Chi-square test, the imputed endpoint will be analyzed using each of the 30 datasets. A pooled test statistic from the chi-square distributed statistics after analyzing each of the 30 imputed datasets will be used to test the difference between upadacitinib group and historical placebo rate with Rubin's strategy. Note that measurements will be considered as missing after receiving antibiotics for HS-related infections or discontinued study drug due to lack of efficacy before MI. Regardless of MI imputed values, subjects receiving antibiotics for HS-related infections or discontinued study drug due to lack of efficacy will be counted as non-responders at later visits.

9.2.2 Continuous Endpoints in Period 1

For continuous endpoints except for DLQI, missing data will be handled using Mixed-Effect Model Repeat Measurement (MMRM).

- MMRM will be conducted using a mixed effect model including observed measurements at all visits. For the comparison with historical placebo change

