9.3 Primary Efficacy Endpoint and Analyses

9.3.1 Primary Efficacy Endpoint

The primary endpoint is the achievement of HiSCR at Week 12. HiSCR is defined as at least a 50% reduction in the total AN count with no increase in abscess count and no increase in draining fistula count relative to Baseline.

The corresponding statistical null hypothesis to the primary endpoint is that there is no difference between upadacitinib 30 mg and historical placebo rate, in the proportion of subjects achieving HiSCR at Week 12.

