13.0 Overall Type-I Error Control

Due to the nature of the phase 2 proof of concept study, all the endpoints will be tested at $\alpha = 0.05$ (1-sided) and no alpha-spending is needed.

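### The SAP declares one-sided 0.05 tests, but Appendix E defines the pooled one-sample p-value as a two-sided probability, about twice the one-sided value when the response rate exceeds the historical rate

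*SAP*

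**What the plan says.** SAP 9.1 states: "All tests will be 1-sided at an alpha level of 0.05". SAP 13.0 repeats the level for all endpoints ("1-sided) and no alpha-spending is needed"). SAP 2.4 and Protocol 7.7 base the sample size on a "one-sample Chi-square test and one-sided alpha = 0.05 significance level". The hypothesis in SAP 2.1 is directional: "The proportion of subjects achieving HiSCR with upadacitinib is greater than that with placebo at Week 12".

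The p-value itself is defined in Appendix E. Section 2.5.2 introduces "The pooled p-value for the hypothesis test based on" the pooled statistic D as the probability that an F variable with l and V degrees of freedom exceeds D. The sample code in 3.0 takes a Pearson chi-square against 0.75/0.25 in each imputed dataset, uses its unsigned square root for the between-imputation term, and ends with "PVAL = 1 - CDF('F', DX, DF, VX".

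SAP 9.4.1 carries the method to NRS30, against 22.5%. SAP 9.2.1 uses it for the multiple-imputation sensitivity analysis: "A pooled test statistic from the chi-square distributed statistics after analyzing each of the 30 imputed datasets will be used". SAP 9.3.2 asks for a point estimate, a p-value and a 95% CI, without saying which p-value.

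**The concern.** A chi-square with 1 degree of freedom is a squared z, so its upper tail counts departures from the historical rate in both directions. The F(1, v) tail is likewise a two-sided t probability. Read against 0.05, the printed p is in effect an upper-side test at about 0.025, and it can also reach 0.05 when upadacitinib does worse than the historical rate.

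The declared level and the printed p-value therefore do not match for the primary and secondary endpoints. A borderline result that meets the stated one-sided rule would print as not significant, and someone would have to decide after database lock whether to halve it. A SAP should settle that in advance.

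**Working it through.** **Inputs.** HiSCR null 25% (SAP 9.3.2); NRS30 null 22.5% (9.4.1); assumed HiSCR rate 57% and n = 40 (2.4); 45 on upadacitinib in the simulations (Appendix F 2.1); K = 30 and l = 1 (Appendix E). The range n = 40 to 48 for HiSCR is an assumption that brackets 40 and 45. Denominators 30 to 45 for NRS30 are an assumption, because the endpoint is limited to baseline NRS of at least 3.

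**The plan's power figure.** Power = Φ[(0.57 − 0.25 − z·√(0.25·0.75/40)) / √(0.57·0.43/40)].
- One-sided 0.05 (z = 1.645): 99.6%, which reproduces the stated figure of more than 95%.
- As Appendix E is written (z = 1.960): 99.1%.
- Exact binomial: 99.6% (15 or more responders) and 99.0% (16 or more).

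**The p-value with nothing imputed.** z = (x − n·p0)/√(n·p0·(1 − p0)). The one-sided p is 1 − Φ(z); the p as written is Pr(χ² > z²), which equals twice that when z > 0.
- HiSCR 15/40: z = (15 − 10)/√7.5 = 1.826; one-sided 0.034, printed 0.068.
- HiSCR 16/40: z = 2.191; 0.014 and 0.028.
- HiSCR 17/45: z = 1.980; 0.024 and 0.048.
- NRS30 14/40: z = (14 − 9)/√6.975 = 1.893; 0.029 and 0.058.
- HiSCR 4/40 (10%, below the historical rate): z = −2.191; printed 0.028, one-sided 0.986.

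**With imputed data.** The 2.5.2 formula was compared with a signed z pooled by Rubin's rules, with 2 or 4 of the subjects imputed at an assumed 50% response probability. The printed p was 2.007 to 2.028 times the one-sided p.

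**HiSCR cut-offs (smallest significant count) and exact size under 25%, nothing imputed**

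| n | One-sided z | As written | Exact one-sided 5% | Size, one-sided z | Size, as written |
|---|---|---|---|---|---|
| 40 | 15 | 16 | 16 | 5.4% | 2.6% |
| 41 | 15 | 16 | 16 | 6.7% | 3.3% |
| 42 | 16 | 17 | 16 | 4.2% | 2.0% |
| 43 | 16 | 17 | 17 | 5.1% | 2.5% |
| 44 | 16 | 17 | 17 | 6.3% | 3.2% |
| 45 | 17 | 17 | 17 | 3.95% | 3.95% |
| 46 | 17 | 18 | 17 | 4.8% | 2.4% |
| 47 | 17 | 18 | 18 | 5.9% | 3.0% |
| 48 | 17 | 18 | 18 | 7.0% | 3.7% |

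The cut-off moves at eight of nine n. Against an exact one-sided 5% test the loss is one count at n = 42 (16/42: printed 0.05001, exact 0.042) and n = 46 (17/46: 0.061, exact 0.048).

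**NRS30.** The cut-off moves at 14 of 16 denominators (not at 32 or 39). A result significant by the exact one-sided test is missed at 33, 36, 40 and 43 (14/40: exact 0.049). At the 46% rate assumed in Appendix F 3.2 and n = 40, exact power is 89.3% as written against 94.1% one-sided.

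**Zero between-imputation variance.** V contains 1/r. If no upadacitinib Week 12 value is missing due to COVID-19, all 30 chi-squares are identical and r = 0. The code then divides by zero, and the SAP states no fallback.

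**The case against.** The strongest reply is that little changes in practice. Most of it stands. At n = 45, the number Appendix F assumes, HiSCR needs 17 responders either way. At seven of the nine n, including 40, the p as written leads to the same decision as an exact one-sided 5% test. At 57% and n = 40 the chance of landing on the one count that flips is 99.6% − 99.0% = 0.6%. The estimate and CI in 9.3.2 would show an unfavourable direction. The trial is a phase 2 proof of concept.

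Halving also has a cost: it takes the exact size above 5% at six of the nine n. It can set p < 0.05 beside a 95% CI that includes zero as well. For 15/40 a Wald interval (an assumption; the SAP names no method) runs from −2.5 to +27.5 points.

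That the code is labelled as a sample does not answer the point, because the method text in 2.5.2 gives the same unhalved formula. That an analyst would halve it anyway is possible, but the SAP does not say so. A division by zero would be noticed, so it is only a missing instruction.

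Three stronger readings are tempting and are not supported:
- A reader might infer an inflated risk of falsely claiming benefit. The error runs the other way: exact size as written is 2.0% to 4.0%.
- A reader might infer that the HiSCR comparison is underpowered. It has about 99% power on either reading.
- A reader might take the null in 9.3.1 ("there is no difference between upadacitinib 30 mg and historical placebo rate") as a further contradiction on sidedness. It is an ordinary point null and is compatible with the directional alternative in 2.1.

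**Conclusion.** The mismatch is real and lies in the current method text as well as the code: the declared tests are one-sided at 0.05, while the defined pooled p is two-sided and unsigned. Above the historical rate it is about twice the one-sided p, so the error is conservative. The severity is minor. Only borderline results are affected: one responder at most for HiSCR, and rather more consequence for NRS30, whose assumed rate lies nearer its cut-off. Sample size and data collection are unaffected. The cut-offs assume nothing imputed, and the ranges of n and of the NRS30 denominator are assumptions.

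**What to change.** In Appendix E 2.5.2 and 3.0:
- Pool signed square roots, negative where a dataset's response rate is below the historical rate.
- Define the one-sided p as PVAL/2 when the pooled rate exceeds the historical rate, and 1 − PVAL/2 otherwise.
- When RX_RESULT = 0, use the ordinary signed one-sample z.
- State that this one-sided p is the deciding p under 9.1, for HiSCR, NRS30 and the multiple-imputation sensitivity analysis.

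In 9.3.2, either add a 90% CI or say that the 95% CI is two-sided and may include zero when the one-sided p is below 0.05. If a 90% CI is added, name a score (Wilson) interval so that it agrees with the test. At 15/40 the 90% Wald lower limit is 0.375 − 1.645·√(0.375·0.625/40) − 0.25 = −0.1 points, while the score limit is +1.1 points.

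State the downside: the halved normal-approximation test has exact size of 5.1% to 7.0% at n = 40, 41, 43, 44, 47 and 48. An exact binomial p from the NRI-NC count may be shown as descriptive support only. That count scores COVID-19 missing values as non-response, so it equals the primary count only when there are none.

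Cost: SAP wording and a few lines of code.
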